## 7.2 General Study Procedures

Before any study-related screening or baseline procedure can be completed, a subject must sign and date the IRB-approved ICF. After informed consent has been obtained, all screening procedures and tests establishing eligibility will be performed. Screening procedures are summarized in the Schedule of Assessments ([Section 7.1](#)).

During the study, every effort should be made to perform study procedures as indicated in the Schedule of Assessments ([Section 7.1](#)). Additional procedures deemed necessary as part of standard of care or as required by local laws and regulations may be performed at the investigator's discretion.

Throughout the study, the permitted time windows for scheduled assessments will be as follows:

**Table 15. Study Visit Windows**

Study Part	Cohort Name	Visit Window	PK Plasma Collection Window	PK Urine Collection Window
Part A	Cohorts 1-2 IV (Part A)	Days 14 & 30: ± 1 day	Days 1-2: ± 10 minutes Days 3-5: ± 1 hour	Day 1: ± 1 hour Days 2-5: ± 2 hours
	Cohorts 3-5 IV (Part A)	Days 14 & 30: ± 1 day	Days 1-2: ± 10 minutes Days 3-6: ± 1 hour	Day 1: ± 1 hour Days 2-6: ± 2 hours
	Cohorts 1-4 PO (Part A)	Days 14 & 30: ± 1 day	Day 1: ± 10 minutes Days 2-5: ± 1 hour	Day 1: ± 1 hour Days 2-5: ± 2 hours
	Cohorts 5-6 PO (Part A)	Days 14 & 30: ± 1 day	Day 1: ± 10 minutes Days 2-5: ± 1 hour	Day 1: ± 1 hour Days 2-5: ± 2 hours
Part B	Cohorts 1-2 IV (Part B)	Days 14 & 30: ± 1 day	Days 1-5: ± 10 minutes Days 6-8: ± 1 hour	Day 5: ± 2 hours
	Cohorts 1-4 PO (Part B)	Days 11, 14, & 21: ± 1 day	Day 1: ± 10 minutes Day 7: ± 10 minutes Days 2-6: ± 1 hour Days 8-10: ± 1 hour	Day 8: ± 2 hours
	Cohorts 5-6 PO (Part B)	Days 11, 14, & 21: ± 1 day	Day 1: ± 10 minutes Day 7: ± 10 minutes Days 2-6: ± 1 hour Days 8-10: ± 1 hour	Day 8: ± 2 hours

Approved

**Table 15. Study Visit Windows**

Study Part	Cohort Name	Visit Window	PK Plasma Collection Window	PK Urine Collection Window
Part C	HFrEF and HFpEF	Not Applicable	Days 1: ± 10 minutes Days 2-4: ± 1 hour Day 5: ± 10 minutes Days 6-8: ± 1 hour Day 9: ± 10 minutes Days 10-16: ± 1 hour Days 17-21: ± 1 hour	Not collected

Page 2 of 2

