**Table 14. Schedule of Assessments for Patient Cohort Part C**

Activity Study Day	10 mg PO Treatment													
	-28 to -2 k	-1	1					2	3	4	5	6	7	
Study Time (Hours)			Pre-dose	0	1	2	4	6	24 G	48 G	72 G	96 G	120 G	144 G
General & Safety Assessments														
Informed Consent J	X													
Medical History	X													
Physical Examination	X	X							X					
Weight	X	X												
Height	X													
Vital Signs (BP E , HR, RR, TEMP) A	X	X	X		X	X		X	X	X	X	X	X	X
ECG B	X		X		X	X	X	X						
Concomitant Medications														
Adverse Events I														
Serious Adverse Events														
Laboratory Assessments														
Chemistry, Hematology, & Urinalysis	X	X							X					
Troponin I	X		X						X		X			
NT-proBNP	X													
FSH (postmenopausal females only) C	X													
Pregnancy C	X	X												
HIV, HepCAb, HBsAg, HBcAb	X													
Drug, Alcohol, & Cotinine Screen	X	X												
Echocardiographic Assessments														
M-mode, 2-D, Flow & Tissue Doppler	X		X					X			X			
Investigational Product AdministrationE														
IP Administration PO (10 mg, Days 1-7)				X					X	X	X	X	X	X
Pharmacokinetic/Biomarker Assessments														
AMG 986 Plasma PK Collection			X		X	X	X	X	X					
Plasma and Serum Biomarker Collection			X											
Cell Pellet Collection			X											

Approved

Footnotes defined on page 75

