**Table 14. Schedule of Assessments for Patient Cohort Part C**

Activity Study Day	30 mg PO									
	8				9	10	11	12	13	14
Study Time (Hours)	168 G (Predose)	170	172	174	192 G	216 G	240 G	264 G	288 G	312 G
General & Safety Assessments										
Informed Consent										
Medical History										
Physical Examination										
Weight										
Height										
Vital Signs (BP E , HR, RR, TEMP) A	X		X		X	X	X	X	X	X
ECG B		X		X						
Concomitant Medications										
Adverse Events I										
Serious Adverse Events										
Laboratory Assessments										
Chemistry, Hematology, & Urinalysis	X				X					
Troponin I	X									X
NT-proBNP										
FSH (postmenopausal females only) C										
Pregnancy C										
HIV, HepCAb, HBsAg, HBcAb										
Drug, Alcohol, & Cotinine Screen										
Echocardiographic Assessments										
M-mode, 2-D, Flow & Tissue Doppler	X			X			X			
Investigational Product Administration										
IP Administration PO (30 mg, Days 8-14) E	X				X	X	X	X	X	X
Pharmacokinetic/Biomarker Assessments										
AMG 986 Plasma PK Collection	X	X	X	X	X					
Plasma and Serum Biomarker Collection	X									
Cell Pellet Collection										

Approved

Footnotes defined on page 75

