**Table 14. Schedule of Assessments for Patient Cohort Part C**

Activity Study Day	100 mg											EOS 30
	15 Predose					16	17	18	19	20	21	
Study Time (Hours)	336 G	337	338	340	342	360 G	384 G	408 G	432 G	456 G	480 G	
General & Safety Assessments												
Informed Consent												
Medical History												
Physical Examination	X										X	X
Weight												
Height												
Vital Signs (BP E HR, RR, TEMP) A	X	X		X		X	X	X	X	X	X	X
ECG B	X	X	X		X							X
Concomitant Medications												
Adverse Events I												
Serious Adverse Events												
Laboratory Assessments												
Chemistry, Hematology, & Urinalysis	X					X					X	X
Troponin I												X
NT-proBNP												
FSH (postmenopausal females only) C												
Pregnancy C												X
HIV, HepCAb, HBsAg, HBcAb												
Drug, Alcohol, & Cotinine Screen												
Echocardiographic Assessments												
M-mode, 2-D, Flow & Tissue Doppler	X				X			X			X	X
Investigational Product Administration												
IP Administration PO (100 mg, Days 15-21) E	X					X	X	X	X	X	X	
Pharmacokinetic/Biomarker Assessments												
AMG 986 Plasma PK Collection	X	X	X	X	X	X					X	
Plasma and Serum Biomarker Collection	X										X	
Cell Pellet Collection												

Approved

Footnotes defined on page 75

- 
- A Vital signs will be performed pre-dose for each day and at time points in the SOA.
  - B ECGs will be performed on Day 1 pre-dose and may be repeated. . At screening a single ECG will be performed. At baseline, a single ECG will be performed. . At all other time points single ECGs will be performed in a standardized method, and prior to blood draws or other invasive procedures.
  - C Female subjects only.
  - D BP measurements will be obtained in a semi-Fowler position at pre-dose and at time points listed in the SOA.
  - E Once daily PO AMG 986/placebo administration for 7 consecutive days.
  - F This assessment will be performed only if deemed necessary by the investigator upon review of the prior assessment.
  - G Procedures to be completed prior to dosing: physical examination, vital signs, ECGs, laboratory assessments, echocardiographic assessments, pharmacokinetic assessments.

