### **7.2.3 Treatment**

Treatment begins when the first dose of protocol-required therapies is administered to a subject. The treatment procedures are to be completed during the Treatment Visits at time points designated in the Schedule of Assessments (Section 7.1).

If any subject stops treatment (eg, due to an adverse event), the subject will be asked to continue to complete protocol-required visits for safety monitoring as determined by the Principal Investigator in consultation with the Amgen Medical Monitor and Amgen Global Safety Officer.

When multiple post dose procedures are required to be conducted at the same nominal time point, the following order of precedence will be used: (1) vital signs, (2) ECGs, (3) PK sample collection, (4) Echocardiogram.

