### **10.5.3 Secondary Endpoints**

#### **10.5.3.1 Pharmacokinetics Analysis (PK)**

Plasma samples will be analyzed for AMG 986 concentrations using a validated assay. Individual concentration-time plots for AMG 986 will be presented for each subject as well as mean concentration-time plots for each cohort. Pharmacokinetic parameters

including but not limited to AUC,  $C_{max}$ , and  $t_{max}$  will be estimated using non-compartmental methods. Actual dosing and sampling times will be used for calculation of PK parameters.

Summary statistics will be generated for each PK parameter for each dose cohort for each Part of the study. A population PK analysis may also be performed to obtain additional PK parameters for each Part of the study.

Bioavailability may also be calculated and summarized if data collected is deemed adequate.

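### The Part C row of Table 15 puts two of its three ±10-minute PK windows on the wrong days, so all post-dose samples at 30 mg and 100 mg fall under ±1 hour

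*Protocol*

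**What the plan says.** Protocol Table 15 (Study Visit Windows) allows Part C plasma PK samples ±10 minutes on Day 1 and ±1 hour on Days 2-4, then "Day 5: ± 10 minutes Days 6-8: ± 1 hour Day 9: ± 10 minutes Days 10-16: ± 1 hour", and ±1 hour on Days 17-21.

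Protocol Table 14 (Part C schedule) has three weekly dose levels: "IP Administration PO (10 mg, Days 1-7"), "IP Administration PO (30 mg, Days 8-14") and "IP Administration PO (100 mg, Days 15-21"). Serial plasma PK is taken on the first day of each level. Footnote G, attached to the 24-h, 168-h and later daily time points, reads "Procedures to be completed prior to dosing: physical examination, vital signs, ECGs, laboratory assessments, echocardiographic assessments, pharmacokinetic assessments", so the single samples on Days 2, 9, 16 and 21 are pre-dose.

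The Part B oral rows of Table 15 show the usual pattern: "Day 1: ± 10 minutes Day 7: ± 10 minutes Days 2-6: ± 1 hour". Days 1 and 7 are the serial-sampling days in Table 13.

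Three other provisions bear on the consequence:
- Protocol 10.5.3.1 says "Actual dosing and sampling times will be used for calculation of PK parameters".
- Protocol 7.2.3 sets the order of post-dose procedures at a shared nominal time as "1) vital signs, (2) ECGs, (3) PK sample collection, (4) Echocardiogram".
- SAP 10.6.1 and 11 (v3.0, after early discontinuation) drop the PK parameter analysis. They keep an individual concentration-time listing and exposure-response plots for stroke volume and ejection fraction.

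**The concern.** A tight window belongs where concentration changes fast, that is, in the hours after a dose. Every Part A and Part B row of Table 15 follows this, and so does Part C on Day 1. At 30 mg and 100 mg, Part C does the reverse. The tight windows sit on a day without a PK sample (Day 5) and a day with only a trough (Day 9), while the post-dose profiles on Days 8 and 15 get the loose window.

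A site could draw these samples up to an hour from nominal without recording a deviation. Part C Cmax and tmax, which are protocol secondary endpoints, would then rest on three or four loosely placed samples per profile. Using actual times dates a sample correctly, but it cannot recover a peak that was not sampled. Any output that showed nominal times would misplace the concentration by up to an hour.

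**Working it through.** No power or alpha calculation is involved. The check maps each plasma PK time in Table 14 to its Table 15 window. Post-dose time is study hour minus 24 × (day − 1); for example, 337 − 24 × 14 = 1 h.

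| Day | Plasma PK in Table 14 | Table 15 window |
|---|---|---|
| 1 (10 mg starts) | pre-dose, 1, 2, 4, 6 h | ±10 min |
| 2 | pre-dose (24 h) | ±1 h |
| 5 | none | ±10 min |
| 8 (30 mg starts) | pre-dose (168 h); 2, 4, 6 h (170, 172, 174 h) | ±1 h |
| 9 | pre-dose (192 h) | ±10 min |
| 15 (100 mg starts) | pre-dose (336 h); 1, 2, 4, 6 h (337, 338, 340, 342 h) | ±1 h |
| 16, 21 | pre-dose (360 h, 480 h) | ±1 h |

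**Count.** Post-dose samples at 30 and 100 mg under ±1 hour: 3 + 4 = 7, which is all of them.

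**Permitted intervals** (nominal ± window):
- Day 15 at ±1 h: 0-2, 1-3, 3-5 and 5-7 h. The first two overlap by 2 − 1 = 1 h, so the 1-h sample may be drawn at dosing or after the 2-h sample. The others meet end to end.
- Day 8 at ±1 h: 1-3, 3-5 and 5-7 h, meeting end to end.
- Day 15 at ±10 min: 0.83-1.17, 1.83-2.17, 3.83-4.17 and 5.83-6.17 h, all separate.

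**Window as a share of nominal time.** At ±1 h: 1/1 = 100%, 1/2 = 50%, 1/4 = 25%, 1/6 = 17%. At ±10 min: 17%, 8%, 4%, 3%.

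**Possible origin.** The Amendment 5 rationale records a change from 4 to 7 days per dose level. Start days are 1 + 4i = 1, 5, 9 under the old plan and 1 + 7i = 1, 8, 15 under the current one. The first set equals the ±10-minute days in Table 15. The earlier Table 15 is not shown, so carry-over is an inference; the mismatch stands on the current tables alone.

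**Near-worst-case illustration of spread.** On Days 8 and 15 the 6-h sample is the only post-dose PK sample that shares a nominal time with an echo. I used a two-compartment oral model with the protocol's CL 45 mL/h/kg, Vss 463 mL/kg and 12-h half-life. The assumptions outside the documents are:
- weight 62.9 kg, chosen because it reproduces Table 1 (AUC24h 0.151 against 0.151 at 0.5 mg), with V1 6.92 L and Q 2.71 L/h;
- ka 0.74/h and 0.99/h, fitted to Table 3 Cmax/AUCinf: 1850/12600 = 0.147/h at 30 mg and 5760/34100 = 0.169/h at 100 mg;
- sampling times uniform over the window.

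Going from ±10 min to ±1 h, the timing CV of the 6-h concentration rises from 2.5% to 14.9% on Day 8 and from 2.3% to about 14% on Day 15. Over 60-80 kg the ±1 h figure is 12.0-15.2%. This is spread in the sampled concentration, not error in a paired concentration-versus-echo plot.

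**The case against.** **The tables do different jobs.** Table 14 gives target times and Table 15 gives tolerances, so a site can comply with both. That is true, but a tolerance for a Day 5 sample that does not exist serves no purpose, and the row departs from every other row. Overlap as such is not unique to Part C: the IV cohorts sample at 0.25 and 0.5 h, and ±10 minutes there overlaps by 10 + 10 − 15 = 5 minutes. The argument rests on where the tight windows sit, not on overlap alone.

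**Little is left to affect.** This objection largely stands. SAP v3.0 drops PK parameters, and SAP 10.6.1 does not say that the exposure-response plots cover Part C Days 8 and 15. In such a plot a late sample still shows the true concentration when drawn, and the procedure order keeps echo after PK.

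**Actual behaviour may be far better than the limit.** Protocol 7.2 asks sites to make every effort to follow the schedule. Uniform timing over ±1 hour is therefore close to a worst case.

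**SAP 10.1 already says which times apply.** It assigns scheduled time points to data summarised by time. It does not clearly reach an individual listing or a scatter plot, and the actual-time rule in Protocol 10.5.3.1 covers only a parameter calculation that is no longer planned. A small gap remains.

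**Stronger readings to avoid.** A reader might infer that dose steps in Part C relied on poorly timed samples. They did not: Protocol 3.1 and 6.2.1.3.1 place the Part C dose level review at the end of dosing. Nor do the documents show that samples were actually mistimed, or that the exposure-response plots are biased.

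**Conclusion.** The Part C row of Table 15 is wrong as written. Day 1 agrees with Table 14; Days 5 and 9 do not. As a result all seven post-dose samples at 30 mg and 100 mg carry ±1 hour, and the first two intervals on Day 15 overlap by an hour. This finding needs no assumption beyond the two current tables.

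The severity is minor. Under the protocol's own analysis, Part C Cmax and tmax would be less precise. Under SAP v3.0 only the concentration-time listing and any Part C exposure-response plots are touched, and the effect on the plots is small provided each echo is paired with the PK sample from the same nominal time. The CV figures are an upper-end illustration that depends on assumed weight, distribution parameters and uniform timing; the conclusion does not rest on them.

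**What to change.** **Protocol Table 15, Part C row.** Set windows by day, as the other rows do: Days 1, 8 and 15 at ±10 minutes; Days 2, 9, 16 and 21 at ±1 hour. Delete the Day 5 entry. State that every pre-dose sample, including those at 168 h and 336 h, is still drawn before dosing as footnote G requires.

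**SAP 10.6.1, for samples already collected.**
- State that the individual concentration-time listing shows actual sampling times.
- State that exposure-response plots pair each echo with the PK sample from the same nominal time. Table 14 has echoes on Days 4, 11 and 18 without a PK sample that day, so say whether these are left out.
- Report actual-minus-nominal sampling times for Days 8 and 15.

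**Cost.** One table row, two or three SAP sentences and one short summary. The row change cannot alter samples taken before the early discontinuation; it corrects the record and any re-use of the table. Only the SAP text and timing summary help with the existing data.

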**Meal Restrictions:**

The clinical site will provide standardized meals to the subjects during the in-house residency period.

Subjects are required to refrain from food and drinks (except water) 8 hours prior to each laboratory measurement.

**Exercise Restrictions:**

Subjects are required to refrain from strenuous exercise during screening, during in-house residency period and 48 hours prior to each outpatient visit.

**7.2.1 Screening**

After informed consent is obtained, screening procedures are to be completed during the screening period at time points designated in the Schedule of Assessments ([Section 7.1](#)).

**For Rescreen Subjects:** A new informed consent form must be signed unless it has been < 30 days since the previous ICF signature was obtained.

**Repeat Assessments:** Screening assessments (eg, vital signs, ECGs, laboratory assessments, cotinine and urine drug screen) may be repeated during screening. The decision regarding whether a subject has failed screening after repeat assessment will be decided on a case-by-case basis at the discretion of the Principal Investigator. The decision to re-screen a subject will be made on a case-by-case basis at the discretion of the Amgen Medical Monitor in consultation with the Principal Investigator.

**7.2.2 Baseline / Day -1**

Baseline is defined as assessments completed on Day -1 or Day 1 pre-dose, when the procedure is performed on Day 1 pre-dose. Subjects will be admitted to the research

facility on the day before IP administration (Day-1). The baseline / Day -1 procedures are to be completed at time points designated in the Schedule of Assessments (Section 7.1).

### **7.2.3 Treatment**

Treatment begins when the first dose of protocol-required therapies is administered to a subject. The treatment procedures are to be completed during the Treatment Visits at time points designated in the Schedule of Assessments (Section 7.1).

If any subject stops treatment (eg, due to an adverse event), the subject will be asked to continue to complete protocol-required visits for safety monitoring as determined by the Principal Investigator in consultation with the Amgen Medical Monitor and Amgen Global Safety Officer.

When multiple post dose procedures are required to be conducted at the same nominal time point, the following order of precedence will be used: (1) vital signs, (2) ECGs, (3) PK sample collection, (4) Echocardiogram.

### **7.2.4 Safety Follow-up Visit(s)/End of Study Visit**

Subjects will return to the clinic for follow-up visits in accordance to the Schedule of Assessments (Section 7.1) and be followed through the completion of the EOS procedures on Day 30. If an EOS test result demonstrates a clinically significant clinical or laboratory abnormality, the subject will be followed until resolution of the abnormality or until it is considered clinically stable by the investigator.

### **7.2.5 Long-term Follow-up**

Not applicable for this study.

### **7.2.6 Demographics**

Demographic data collection including sex, age, race, and ethnicity will be collected in order to study their possible association with subject safety and association to AMG 986.

### **7.2.7 Medical History**

The investigator or designee will collect a complete medical history from birth to enrollment at screening and other times shown in Section 7.1. Any unresolved medical history will be graded according to Common Terminology Criteria for Adverse Events CTCAE version 4.0 (Appendix A) unless specified otherwise. Medical history will include information on the subject's concurrent medical conditions. All findings will be recorded on the relevant CRF.

Approved

### 7.2.8 Physical Examination

The investigator or qualified designee will perform a physical examination at the time points indicated in [Section 7.1](#). Pre-dose abnormal findings will be reported on the medical history CRF. Any adverse change from the Baseline physical examination (Screening and Day -1 physical examination) will be documented on the Event CRF.

### 7.2.9 Physical Measurements

Height measurement (in cm and without shoes) and weight measurement (in kg and without shoes) will be obtained. Body mass index (BMI) will be calculated using height and weight measurements taken at screening and using the following formula:

$$\text{BMI (kg/m}^2\text{)} = \text{weight (kg)} / [\text{height (cm}/100\text{)}]^2$$

### 7.2.10 Vital Signs

Safety vital signs will be recorded by the investigator or designee at time points specified in [Section 7.1](#).

The following measurements must be performed: systolic/diastolic BP, HR, respiratory rate, and temperature.

Blood pressure will be measured in the following manner:

- Subjects should be lying in a semi-Fowler position quietly and comfortably for at least 5 minutes. The upper arm should be bare without constrictive clothing and supported at heart level.
- An appropriately sized cuff (cuff bladder encircling at least 80% of the arm) should be used to ensure accuracy. Neither the subject nor the observer (measurer) should talk during measurement.

In Parts A and B, BP measurements will be performed in a standardized method in triplicate approximately 2 minutes apart. Triplicate measurements of BP will be obtained at pre-dose and at time points corresponding to ECG monitoring. At time points in which ECG monitoring is not performed, single measures of BP will be obtained as part of the safety vital signs monitoring. In Part C, single BP measurements will be performed in a standardized method at pre-dose and at time points corresponding to ECG monitoring. At time points in which ECG monitoring is not performed, single measures of BP will be obtained as well. PK sample collection should occur after blood pressure measurements and ECG monitoring are completed.

Respiratory rate will be assessed by a full minute count. Abnormal measurements maybe repeated at the investigator's discretion. All data collected will be entered on the CRF.

The temperature location selected for a subject should be the same that is used throughout the study and documented on the vital signs CRF.

Record all measurements on the vital signs CRF. Abnormal measurements may be repeated at the discretion of the investigator and must be reported on the corresponding CRF page. When vital signs and blood sample collection occur at the same time, vital signs should be performed before blood samples.

#### **7.2.11 Serum Follicle-stimulating Hormone Test (Females Only)**

Additional serum will be collected for an FSH test for females at screening. Females must be of non-reproductive potential (ie, postmenopausal – age of  $\geq 55$  years with no spontaneous menses for at least 12 months, or age of  $< 55$  years with no menses for at least 12 months AND with postmenopausal gonadotropin levels (follicle-stimulating hormone levels  $> 40$  IU/L or according to the definition of “postmenopausal range” for the laboratory involved) OR history of hysterectomy; OR history of bilateral oophorectomy OR history of bilateral salpingectomy).

Results must be consistent with postmenopausal status per local laboratory ranges for inclusion in this study. Postmenopausal status will be recorded on the medical history CRF.

